#### **11.4. Enrollment Controls**

According to the study protocol, 10 ICD subjects (at least 2 single chamber ICDs and 2 dual chamber ICDs) and 10 CRT-D subjects will be enrolled. It should be ensured that at least 8 ICD subjects (at least 1 single chamber ICD and 1 dual chamber ICD) and 8 CRT-D subjects undergo protocol required MR scan and complete all the sequences. It should be ensured that both single coil and dual coil defibrillation leads are implanted. It should be ensured that both straight and spiral LV leads are implanted. Subject enrollment might be expanded to meet the above requirement to support product registration.

Generally, one individual center may not enroll more than 10 subjects. Investigational sites will be notified when the enrollment goal is close to being reached and once enrollment is complete.

#### **11.5. End-of-Study Action Plan**

Phase I is completed when all the subjects finish MRI + 1 Month Visit, and the data will be summarized to support product CFDA registration. All subjects will be followed-up till 1 year post implantation in Phase II. After that, subjects will receive routine clinical practice at each center.

### **12. Study Methods**

#### **12.1. Data Collection**

The data collection schedule for the MR ICD study is shown in Table 12-1.

#### **12.2. Study Candidate Screening**

For the MR ICD Study, physician investigators are responsible for screening all potential patients and selecting those who are appropriate for study inclusion. The patients selected for participation should be from the investigator's general patient population.

#### **12.3. Informed Consent**

Patients who appear to meet all of the inclusion criteria and none of the exclusion criteria and agree to participate in the MR ICD study must give written informed consent approved by

the EC prior to study participation and use of any investigational product or testing/ data collection. Patients who sign informed consent for the MR ICD study will be considered enrolled in the study at the point of executing an ICF.

#### **12.4. Enrollment Visit**

The data to be collected during enrollment into the MR ICD study comprise of subject demographic data including age, ethnicity and gender, medical history including arrhythmia history, cardiac disease history, and current cardiovascular medications, a physical assessment of the subject including height, weight, heart rate and blood pressure.

If the subject has metal objects in body, radiologist approval to undergo MRI scan should be documented. A pregnancy test must be performed within 7 days prior to the index procedure in women of child-bearing potential.

##### **12.4.1. Enrollment Source Data Requirements**

Source data requirements at Enrollment are described in Table 12-2.

**Table 12-1 Data Collection Schedule**

Procedure /Assessment	Enrollment	Implant	Pre-Discharge	MRI Visit	MRI+ 1Month Visit	MRI+ Every Three-Month Visits	Implant+ 1Year Visit	Additional Visits	Medically necessary MRI
Timeframe	≤ 30 days prior to Implant	Implant Day 0	3-72 hours from Implant	6-9 weeks from Implant a	30 ± 7 days from MRI Visit	90 ± 14 days from MRI Visit b	365±45 days from implant		
Informed consent	X								
Demographics	X								
Medical history	X								
Physical assessment	X								
Pregnancy test	X								
Device implant		X							
MR Scan				X					X
Device evaluation		X	X	X pre&post	X	X	X	O	O
Beeper evaluation				X pre&post					X pre&post
Save all				X	X		X	O	O
Printout of device settings and history		X	X	X	X	X	X	X	X
Adverse events	X	X	X	X	X	X	X	X	X

a must occur at least 6 weeks after surgical revision of the ImageReady System

b The first Every 3-month visit will occur 90 ± 14 days after MRI visit. Subsequent Every 3-month follow-up visits will be scheduled every three months (90 days ± 14 Days) from the previous scheduled study follow-up.

c A pregnancy test must be performed within 7 days prior to the index procedure in women of child-bearing potential.

**Table 12-2 Enrollment Source Documentation Requirements**

Source Documentation Requirement	Disposition
Informed consent form and process	Retain at center
Demographic, Medical history and Physical assessment	
Completed Radiologists Technical Source Form (applicable for subjects with metallic implants only)	
Adverse events	

## 12.5. Implant

The implant procedure will occur either on the same day as enrollment, after the subject signs and dates the informed consent form, or up to 30 days later.

To satisfy the MRI Conditions of Use (see Section 6), the PG must be implanted in the left or right pectoral (subcutaneous or sub-muscular) regions. The implant procedure end time is defined as the time of device pocket closure. Record the end time in the electronic data capture (EDC) system.

### 12.5.1. Device Evaluation

All implanted leads will be evaluated through the implanted PG using the test parameters listed in Table 12-3:

- Manual pacing threshold tests, as defined in sections 12.5.1.1, 12.5.1.2 and 12.5.1.3.
- Sensing amplitude
- Impedance
- Shock impedance (RV lead only)

Record the measurements in the EDC system.

**Table 12-3 Test Parameters**

Description	RA Threshold Test	RV Threshold Test	LV Threshold Test
Test Type	Amplitude	Amplitude	Amplitude
Pulse Width (ms)	0.5	0.5	0.5
Cycles per Step	3 (minimum)	3 (minimum)	3 (minimum)
Pacing Lead Configuration	Not Programmable	Not Programmable	Per HCP For MRI and MRI + 1 Month visits: The same LV Pacing Configuration must be used for threshold testing

Impedance Tests	RA Impedance Test	RV Impedance Test	LV Impedance Test
Pacing Lead Configuration	Bipolar	Bipolar	Same LV configuration as the Pacing Test  For MRI and MRI +1 Month visits: The same LV Pacing Configuration must be used for impedance testing
Sensing Tests	RA Sensing Test	RV Sensing Test	LV Sensing Test
Sensing Configuration	Bipolar	Bipolar	Per HCP For MRI and MRI+1 Month visits: The same LV Sensing Configuration must be used for sensing testing
Shock Impedance Tests		RV Shock Impedance Tests	
		Per HCP For MRI and MRI+1 Month visits: The same RV Shock Impedance Configuration must be used for impedance testing	

Note: Mode, Lower Rate Limit, Amplitude, Paced AV delay and LV Pacing Lead Configuration shall be set per physician or HCP discretion.

#### 12.5.1.1. Manual Right Atrial Threshold Test

If the subject does not have an active implanted RA lead, then skip to the next section.

Otherwise, perform a manual RA threshold test following these steps, unless the testing is inhibited by a patient condition (example: subject is in atrial fibrillation):

1. In the Atrial Threshold Test screen set the Test Type to Amplitude
2. Mode, Lower Rate Limit, Amplitude and Paced AV delay shall be set per physician or HCP discretion

3. Pulse Width shall be set to 0.5 ms
4. Cycles per Step shall be set to a minimum of 3
5. Start the annotated real-time ECG from the PRM, then start the manual RA threshold test
  - 1) A count of 2 non-capture beats at a given voltage level is required to declare loss of capture (LOC)
  - 2) If the subject experiences discomfort during the threshold test due to extracardiac stimulation, then stop the test and perform the manual threshold test per physician discretion.
6. When LOC is determined, stop the threshold test. Stop the PRM real-time ECG a minimum of 2 seconds after LOC is determined.
7. Label the PRM ECG with the subject ID#, date, Visit name, and “Manual RA threshold test”.
8. The threshold for the manual RA threshold test is defined as one voltage level above the level where the 2 non-captured beats are observed. Record the threshold in the EDC system.
9. If the threshold saved on the PRM does not match the threshold, as defined in step 8, then update the RA Pace Threshold in the programmer.

#### **12.5.1.2. Manual Right Ventricular Threshold Test**

Perform a manual RV threshold test following these steps:

1. In the Right Ventricular Threshold Test screen set the Test Type to Amplitude
2. Mode, Lower Rate Limit, Amplitude and Paced AV delay shall be set per physician or HCP discretion
3. Pulse Width shall be set to 0.5 ms
4. Cycles per Step shall be set to a minimum of 3
5. Start the annotated real-time ECG from the PRM, then start the manual RV threshold test
  - 1) A count of 2 non-capture beats at a given voltage level is required to declare loss of capture (LOC)

- 2) If the subject experiences discomfort during the threshold test due to extracardiac stimulation, then stop the test and perform the manual threshold test per physician discretion.
6. When LOC is determined, stop the threshold test. Stop the PRM real-time ECG a minimum of 2 seconds after LOC is determined.
7. Label the PRM ECG with the subject ID#, date, Visit name, and “Manual RV threshold test”.
8. The threshold for the manual RV threshold test is defined as one voltage level above the level where the 2 non-captured beats are observed. Record the threshold in the EDC system.
9. If the threshold saved on the PRM does not match the threshold, as defined in step 8, then update the RV Pace Threshold in the programmer.

#### **12.5.1.3. Manual Left Ventricular Threshold Test**

If the subject does not have an active implanted LV lead, then skip to the next section. If multiple manual LV threshold tests are performed, then record the manual LV threshold test that matches the final programmed LV lead configuration following these steps:

1. In the Left Ventricular Threshold Test screen set the Test Type to Amplitude
2. Mode, Lower Rate Limit, Amplitude and Paced AV delay shall be set per physician or HCP discretion
3. Pulse Width shall be set to 0.5 ms
4. Cycles per Step shall be set to a minimum of 3
5. Start the annotated real-time ECG from the PRM, then start the manual LV threshold test
  - 1) A count of 2 non-capture beats at a given voltage level is required to declare loss of capture (LOC)
  - 2) If the subject experiences discomfort during the threshold test due to extracardiac stimulation, then stop the test and perform the manual threshold test per physician discretion.
6. When LOC is determined, stop the threshold test. Stop the PRM real-time ECG a

minimum of 2 seconds after LOC is determined.

7. Label the PRM ECG with the subject ID#, date, Visit name, and “Manual LV threshold test”.
8. The threshold for the manual LV threshold test is defined as one voltage level above the level where the 2 non-captured beats are observed. Record the threshold in the EDC system.
9. If the threshold saved on the PRM does not match the threshold, as defined in step 8, then update the LV Pace Threshold in the programmer.

#### **12.5.2. Completing the Implant Visit**

1. Program the device according to physician discretion
2. Print the ‘Quick Notes’ Report

#### **12.5.3. Implant Source Data Requirements**

Source data requirements at implant are described in Table 12-4.

**Table 12-4 Implant Source Documentation Requirements**

Source Documentation Requirement	Disposition
Device model/serial number	Retain at center
Lead model/serial numbers for all implanted leads	
Device Evaluation (pace thresholds, sense amplitudes, impedances, RV shock impedance)	
PRM ECG strips from manual threshold tests documenting LOC for all implanted leads	
Printout of ‘Quick Notes’ Report	
Adverse Events	

### **12.6. Pre-Discharge**

#### **12.6.1. Device Evaluation**

The Pre-discharge Visit will occur either on the same day as the ImageReady System implant procedure, a minimum of 3 hours after pocket closure, or up to 72 hours after the implant procedure.

All implanted leads will be evaluated through the implanted PG using the test parameters listed in Table 12-3:

- Manual pacing threshold tests, as defined in sections 12.5.1.1, 12.5.1.2 and 12.5.1.3.
- Sensing amplitude
- Impedance
- Shock impedance (RV lead only)

Record the measurements in the EDC system.

### **12.6.2. Completing the Pre-Discharge Visit**

1. Program the device according to physician discretion
2. Print the 'Quick Notes' Report
3. Schedule the MRI follow-up visit.

### **12.6.3. Pre-Discharge Source Data Requirements**

Source data requirements at Pre-discharge Visit are described in Table 12-5.

**Table 12-5 Pre-Discharge Source Documentation Requirements**

Source Documentation Requirement	Disposition
Device Evaluation (pace threshold, sense amplitude, impedance, RV shock impedance)	
PRM ECG strips from manual threshold tests documenting LOC for all implanted leads	Retain at center
Printout of 'Quick Notes' Report	
Adverse Events	

## **12.7. MRI Visit**

The MRI Visit will occur 6 to 9 weeks (42-63 days) after implant or surgical revision ((i.e., a lead revision/ reposition) of the ImageReady System implant.

### **12.7.1. Device Evaluation Prior to Commencement of MR Scan**

1. All implanted leads will be evaluated through the implanted PG for **THREE separate consecutive sets of measurements** using the test parameters listed in Table 12-3:

- Manual pacing threshold tests, as defined in sections 12.5.1.1, 12.5.1.2 and 12.5.1.3.
- Sensing amplitude
- Impedance
- Shock impedance (RV lead only)

2. Test for phrenic nerve stimulation (PNS) and measure the PNS threshold if detected in the programmed LV lead configuration
3. Perform an evaluation of Beeper function as defined in section 12.7.1.1.
4. Print the 'Quick Notes' Report

Record the measurements in the EDC system.

#### **12.7.1.1. Evaluation of Beeper function**

To test if the Beeper is audible,

1. Program Magnet Response to Inhibit Therapy
2. Place the magnet over the PG for a minimum of 5 seconds but not for more than 20 seconds in a quiet environment.
  - If the Tachy mode is programmed to 'Monitor + Therapy': A short beep may be heard once every second, as long as the magnet is placed over the PG.
  - If the Tachy mode is programmed to 'Monitor only' or 'OFF': A continuous beep may be heard as long as the magnet is placed over the PG.

Note: The Magnet Sensor will detect magnets (donut, horseshoe or wrist) within 3 cm.

The Magnet Sensor will detect a  $60 \text{ G} < \text{field} \leq 300 \text{ G}$ , when applied perpendicularly to the surface of the PG, either face.

3. The subject and the HCP will be asked to indicate whether the Beeper is audible to them.
4. If not audible, by either the subject or the HCP, a second attempt at evaluating Beeper function will be performed. The Beeper should be assessed in the alternate Tachy mode (as listed in step 2) if tolerated by the subject.
5. Record if the Beeper was audible by the subject and the HCP in the EDC.

#### **12.7.2. Subject Evaluation Prior to Commencement of MR Scan**

##### **12.7.2.1. Confirmation of MRI Conditions of Use**

Subjects must meet the MRI Conditions of Use, comprised of Cardiology and Radiology Conditions of Use, as listed in the *BSC MRI Technical Guide* and Section 6 of this protocol.

#### **12.7.2.2. Heart Rhythm Monitoring prior to MRI protection mode programming**

It is **required** that the heart rhythm be monitored by the site Principal Investigator or a subinvestigator for all subjects prior to initiation of the MRI Protection Mode and the MR Scan. Heart rate and any abnormal rhythms, including incidence of ectopy shall be documented. Any abnormal rhythms / ectopy shall be documented with a printed ECG or rhythm strip if possible.

#### **12.7.3. MR Scans**

The MR scan must be performed within the guidelines of this protocol and the *BSC MRI Technical Guide*. When differences exist, the ENABLE MRI Study protocol extends the *BSC MRI Technical Guide*.

MRIs must be performed in 1.5 Tesla, closed bore scanners with body coil excitation. Subjects will complete MR scans per the MR scan sequences protocol in Section 29 of this protocol.

**Note:** Incidental findings are defined as a “finding concerning an individual research participant that has potential health or reproductive importance and is discovered in the course of conducting research but is beyond the aims of the study”. The MR scans required by the ENABLE MRI Study are not intended for diagnostic purposes. Therefore, they are not intended or required to be read by trained radiologists. If the site’s MR technician performing the scan determines any incidental findings, or if a site’s procedures dictate that MR scans must be read, any incidental findings must be reported to the site’s primary investigator by the person who reads the scan.

#### **12.7.3.1. Programming MRI Protection Mode**

Prior to undergoing an MR scan, the ImageReady System must be programmed to the MRI Protection Mode and an appropriate pacing mode is set using the PRM. The PRM is to be kept ON and in MRI Zone I or II as close to the MRI room as possible.

WARNING: The PRM is MR Unsafe and must remain outside the MRI site Zone III (and higher) as defined by the American College of Radiology Guidance Document for Safe MR Practices. Under no circumstances should the PRM be brought into the MRI scanner room, (Zone IV), or the control room (Zone III). Programming the PG to MRI Protection Mode

should be done as close to the planned start of the MR scan as possible.

1. Start monitoring the subject
2. Program the MRI Protection Time-out (nominal setting: 6 hours; programmable values are OFF, 3, 6, 9, 12 hours)
3. Program the PG to the MRI Protection Mode, set up appropriate pacing parameters
4. Print the MRI Protection Settings Report. This report documents the MRI Protection Mode settings and details.
  - a. If the Time-out feature is used, the report includes the exact time and date when MRI Protection Mode will expire. If the Time-out feature is used, the MRI technologist/radiologist must verify that adequate time remains to complete the scan and to exit the MR scanner room.

Please refer to the *BSC MRI Technical Guide* for more information regarding PG MRI Protection Mode programming and other associated MRI warnings, cautions, and potential adverse events.

#### **12.7.3.2. Monitoring of Subjects during the MRI Protection Mode**

Subjects must be continuously monitored by the site Principal Investigator or a sub-investigator for the entire duration of the MR scan. **For the entire duration of the MR scan, the following will be performed:**

1. Continuous ECG monitoring of the subjects
2. Ensure that an external defibrillator and medical personnel trained in external defibrillation and cardiopulmonary resuscitation (CPR) are present
3. Subjects must be continuously monitored by the site Principal Investigator or a sub-investigator using ECG, along with maintaining voice and visual contact.
4. In addition, **for the entire duration of the MR scan**, the following will be performed:
  - a. The heart rate will be documented in  $5 \pm 2$  minutes intervals.
  - b. ECG alarms must be ON.
  - c. It is recommended that a rhythm strip is printed at each interval.

- d. If there are any abnormal rhythms, a rhythm strip to document the abnormal rhythm should be printed if possible

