### **5.1. MRI Protection Mode**

Prior to an MRI scan, the pulse generator (PG) must be programmed to the MRI Protection Mode using the Programmer / Recorder / Monitor (PRM).

Pacing mode options include asynchronous pacing (DOO, AOO, VOO) or no pacing (Off).

Asynchronous pacing should only be used if the subject is pacing-independent. If MRI Protection Brady Mode is programmed to Off, the subject will not receive therapy until MRI Protection Mode is exited. Off should only be used if the subject is judged to be clinically capable of receiving no pacing during the time the pulse generator is in MRI Protection Mode, including during the scan.

Considerations prior to choosing asynchronous pacing include:

- Determine whether the patient is pacing-dependent.
- Determine which chamber(s) need to be paced.
- Consider the possibility of arrhythmia induction with asynchronous pacing.
- Subjects with the following conditions may have increased risk of developing transient pacing-dependence:
  1. At risk for intermittent AV block (for example, those with progressive AV block, or a history of unexplained syncope)
  2. At risk for trifascicular block (alternating bundle branch block or PR interval > 200 ms with LBBB or other bifascicular block)

In the MRI Protection Mode, the following features and functions are suspended:

- Bradycardia sensing
- Tachycardia detection and therapy
- PaceSafe™ automatic threshold(s)
- Daily diagnostics (Lead Impedance, Intrinsic Amplitude, Pace Threshold)
- Motion and respiratory sensors
- Magnet detection
- RF telemetry
- Battery voltage monitoring
- Beeper is disabled

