***NOTE: In MRI Protection Mode there is no antitachycardia therapy available.***

Refer to the *BSC ImageReady MR Conditional Defibrillation System MRI Technical Guide*, here referred to as the *BSC MRI Technical Guide*, for additional information

regarding MRI Protection Mode.

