### **5.2. MRI Protection Mode Time-out Function**

The MRI Protection Mode Time-out function allows the user to choose the length of time the PG remains in the MRI Protection Mode before returning to previous settings. MRI Protection Mode is programmed using the PRM. The Time-out feature has programmable values of OFF, 3, 6, 9 and 12 hours. At the conclusion of the programmed duration the PG returns to the previously programmed therapy parameters and settings. MRI Protection Mode may also be exited manually at any time during the time-out period. If the MRI Protection Time-out value is programmed to OFF, the patient will not receive Bradycardia pacing, Cardiac Resynchronization Therapy, or Tachycardia therapy until the PG is programmed out of MRI Protection Mode and back to previous operation. Refer to the BSC MRI Technical Guide for additional information on the MRI Protection Mode Time-out Function.

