#### **12.7.3.4. Exiting the MRI Protection Mode**

Upon completion of the MR scan, program the PG out of the MRI Protection Mode. It is recommended to program the PG out of MRI Protection Mode as close to the end of MR scan as possible.

- Document the Time of exiting MRI Protection Mode.

Note: The PRM is MR Unsafe and must remain outside the MRI site Zone III (and higher).

Under no circumstances should the PRM be brought into the MRI scanner room, the control room, or the MRI site Zone III or IV areas.

Upon exiting the MRI Protection Mode, all parameters are restored to pre-MRI Protection Mode values with two exceptions:

- Restoration of function of the Minute Ventilation (MV) sensor is delayed. If MV was programmed to ON or Passive at the time of entry into MRI Protection Mode, upon exit from the mode, an automatic six hour calibration of the sensor will begin. MV-driven rate response is not available during this calibration period. If MV-driven rate response is desired sooner, a manual calibration can be performed.

- The Beeper will remain OFF upon exiting MRI Protection Mode.

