### **13.1.2. Primary Effectiveness Endpoint 1: Pre-MR Scan vs. 1 Month Post-MR Scan RV shocking impedance**

The normal RV shocking impedance measured by the system should be  $\leq 200$  Ohm, with  $>200$  Ohm considered abnormal. The primary effectiveness endpoint 1 is defined as that the average RV shocking impedance is  $>200$  Ohm 1 month post scan, while it is  $\leq 200$  Ohm before scan.

There is no hypothesis testing in the MR ICD study, and it can be considered reasonable if up to 2 failed cases of primary effectiveness endpoint 1 occur.

The data set for the primary effectiveness endpoint 1 will only include subjects who undergo the study-required MR scan and complete all the sequences, and will not include subjects that meet any of the following exclusions:

- Has a medically necessary scan between implant and the MRI + 1 Month Visit
- Fails to meet labeled MRI Conditions of Use
- Experiences a lead-related complication between MRI Visit and the MRI + 1 Month Visit

The time window for MRI + 1 Month visit is  $30 \pm 7$  days post MR scan, so it will capture events within at least 23 days post scan. In this small sample size study, missing data will be excluded.

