5. The suggested duration of all sequences are guidelines for the MR Technician running the scan. Variations from the suggested duration for each of the individual sequences are not to be considered as deviations from the protocol provided the overall scan durations for the RF-intensive and gradient-intensive scan regimens are adhered to (e.g. 11.5 minutes minimum and a maximum of 14 minutes for the RF intensive scan regimen, 17 minutes minimum and a maximum of 21 minutes for the gradient -intensive scan regimen). Active scan time must not be greater than 35 minutes. Pre-scan time does not count towards the required duration.

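### Section 12.7.3.2 requires ECG and external-defibrillator cover only for the MR scan, although tachycardia therapy stays off until MRI Protection Mode is exited

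*Combined protocol and SAP*

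**What the plan says.** Section 12.7.3.2 carries a heading about monitoring while the device is in MRI Protection Mode. Its opening sentence reads: "Subjects must be continuously monitored by the site Principal Investigator or a sub-investigator for the entire duration of the MR scan". The lead-in to the numbered list repeats that limit. Under it come continuous ECG (item 1), an external defibrillator with staff trained in defibrillation and CPR (item 2), investigator monitoring with voice and visual contact (item 3), and a heart-rate record every 5 ± 2 minutes with ECG alarms on (items 4a and 4b).

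Section 5.1 lists the functions suspended in the mode, among them "Tachycardia detection and therapy", and adds the note "In MRI Protection Mode there is no antitachycardia therapy available".

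On ending the mode, section 12.7.3.4 says "Upon completion of the MR scan, program the PG out of the MRI Protection Mode". It recommends doing so close to the end of the scan and requires the exit time to be documented. It also bars the programmer from Zones III and IV. Section 12.7.3.1 says of the programmer: "The PRM is to be kept ON and in MRI Zone I or II as close to the MRI room as possible". Section 5.2 describes an automatic backstop: "At the conclusion of the programmed duration the PG returns to the previously programmed therapy parameters and settings". The time-out can be set to OFF, 3, 6, 9 or 12 hours, with 6 hours nominal (12.7.3.1).

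**The concern.** The patients have an ICD or CRT-D, and their defibrillator therapy is switched off for a scan done for research. Until the mode ends, external rescue is their protection against VT or VF. The protocol treats the whole mode as the period at risk. Exclusion criterion 4 asks whether the subject can tolerate absent tachycardia therapy for as long as the device is in the mode. Section 20.3 lists arrhythmia induction, syncope and death as possible even when the Conditions of Use are met, and warns that competitive pacing may raise arrhythmia risk until the device is reprogrammed.

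The section that lists the rescue duties sets a shorter required period than that. A site that follows the body of 12.7.3.2 rather than its heading could meet the text in full and still have no ECG or defibrillator at hand during transfer to the programmer.

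**Working it through.** No sample-size, power or estimation figure is involved, so the check sets the sections side by side.

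1. **Required period of cover.** The opening sentence and both lead-ins in 12.7.3.2 tie the duties to the MR scan. Sections 6.1 (item 4) and 6.2 (item 6) also tie ECG to the scan.
2. **Period without therapy.** Under 5.1, tachycardia detection and therapy are off for the whole mode.
3. **Can the scan be read as lasting until mode exit?** No. Section 12.7.3.3 (item 7) records the time of scan completion, section 12.7.3.4 records the time of exit, and section 13.2.4 summarizes the interval between the two. The protocol treats them as separate times.
4. **Can exit coincide with scan end?** Not by programmer. It must stay out of the scanner room and control room (12.7.3.1, 12.7.3.4), so the subject comes out first. The time-out is the other route, but its shortest setting is 3 hours.
5. **What else covers the interval?**
   - Step 1 of 12.7.3.1 starts monitoring before the mode is programmed. It names no method, no defibrillator and no end.
   - Sections 6.1 and 6.2 ask for external rescue as backup with no time window of its own, in an item about ECG during the scan.
   - Section 12.7.3.4 directs exit once the scan is complete. Promptness is recommended, and no maximum is set.
   - Section 20.4 asks in general terms for close monitoring during research procedures.
   - None of these says that ECG and defibrillator cover continues until exit.
6. **How many subjects?** Every scanned subject: 20 planned, and at least 8 ICD + 8 CRT-D = 16 who complete all sequences (13.3).
7. **How long?** The documents do not say. Section 29.3 states "Active scan time must not be greater than 35 minutes", and the two regimens give 11.5 + 17 = 28.5 minutes at least and 14 + 21 = 35 minutes at most. Those figures describe active scanning, not the interval after it, and do not measure the gap. The trial will itself record the interval through 13.2.4.
8. **Why the place of the fix matters.** The effectiveness sets drop any subject who "Fails to meet labeled MRI Conditions of Use" (13.1.2 to 13.1.6, 13.4.3; SAP 4.1). If the longer duty were written into 6.1 or 6.2, a brief ECG lapse in transfer could remove a subject. At the planned minimum, one subject is 1/16 = 6.25% of the RV sets and 1/8 = 12.5% of the LV sets, before any other exclusion.

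**The case against.** The strongest reply is that 12.7.3.2 sets a minimum and nowhere tells staff to stop. Its heading names the mode, monitoring starts before the mode is programmed with no stated end, and the backup requirement in 6.1 and 6.2 has no time limit. The investigator, trained staff and a defibrillator are already present when the scan ends, the programmer is nearby and switched on, exit is directed at once, and subjects who could not tolerate absent therapy are excluded. The scan must also follow the sponsor's MRI Technical Guide (12.7.3). Section 6 says that the protocol extends the Guide where they differ, so silence in the protocol would not cancel a duty in the Guide.

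Most of this stands, and it limits the weight of the point. A reader might infer that the protocol directs sites to withdraw cover at scan end. The text does not say that, and nothing shows that any site would do it. Nor can it be concluded that sites lack an instruction altogether, because the Guide was not available. What remains is narrower: the one section that spells out the ECG and defibrillator duties gives them a window that ends before therapy returns, and no other section of the protocol closes it in specific terms.

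**Conclusion.** The point holds as a minor patient-safety wording gap. The protocol names no ECG or external-defibrillator duty between scan end and mode exit, although tachycardia therapy is still off. At a compliant site the interval should be short, but its length is not stated and is not estimated here.

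Two stronger readings should be set aside:

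- A reader might use the time-out to suggest hours of exposure. With the nominal 6-hour setting and 35 minutes of active scanning, 360 − 35 = 325 minutes would remain, and with the time-out OFF there is no limit. Either case requires the directed exit to be missed altogether, so these are ceilings and not expected durations.
- A reader might infer harm to the trial's results. No endpoint, analysis set or estimate depends on this wording.

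The conclusion rests on the protocol text alone and assumes that the device is taken out of the mode by programmer outside Zones III and IV, as 12.7.3.4 directs. If the Guide already requires cover until exit, the change only aligns the protocol with it.

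**What to change.** In 12.7.3.2, require continuous ECG monitoring with alarms on (items 1 and 4b) and an external defibrillator with trained personnel (item 2) from programming into MRI Protection Mode until the mode is exited. Add one matching line in 12.7.3.4. The other items can stay tied to the scan.

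Leave the labeled Conditions of Use in 6.1 and 6.2 as they are. A lapse in the added interval is then a protocol deviation under section 16 and does not remove a subject from the effectiveness sets.

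Section 12.12 takes its flow from 12.7 and allows medically necessary scans at non-investigational sites. There, make the extended cover a recommendation.

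The cost is a few more minutes of cover by staff already present, a portable monitor-defibrillator for the transfer where needed, and possibly some extra deviation records. Because the change concerns subject safety, section 15 calls for an amendment with ethics committee approval before use. No new endpoint data are needed, since the exit time is already documented.
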